2. ANALYSIS SETS

2.1 Definition of analysis sets

Full analysis set (FAS)

The FAS will include all subjects who received at least one dose of study drug, irrespective of whether some of these subjects may have discontinued treatment prior to the trial's end.

RP analysis set (RPAS)

The RPAS will be a subset of FAS, which included FAS subjects who actually received RP surgery.

The analysis of assessments related to RP or post RP will be conducted based on RPAS, except for analysis for primary endpoint. Where denominator of actual rate of radical resection following neoadjuvant hormonal therapy (NHT) will be based on number of subjects in FAS.

2.2 Protocol deviations

All protocol deviations (major and minor) will be reviewed and listed. The list of protocol deviations will be finalized and documented before the database lock. The number and percentage of subjects with protocol deviations (major/minor) will be summarized by protocol deviation category based on FAS. Major deviations will be those which are considered to potentially impact upon the interpretation of the primary endpoint in the study. Major deviations will be listed separately.

3. PRIMARY AND SECONDARY VARIABLES

3.1 PRIMARY ENDPOINT

• Actual radical prostatectomy rate

Actual radical prostatectomy rate is defined as the percentage of the subjects who actually received radical prostatectomy after receiving NHT, including those who early discontinued from treatment. Denominator will be based on number of subjects in FAS.

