3.7.4 Completion of the study

For subjects who received RP, it will be considered as completion of the study if the subjects completed the 3 months post-surgical follow-up period. If the subjects who actually can not receive radical prostatectomy within 30 days after 24 weeks neoadjuvant therapy, it will be considered as completion of the study and reason for failure to operate will be collected.

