5.1 Efficacy assessments

5.1.1 Actual radical prostatectomy rate

Actual radical prostatectomy rate is defined as the rate of the subjects who perform radical prostatectomy after NHT

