8.3 Definitions of analysis sets

Full analysis set (FAS)

The FAS will include all subjects who received at least one dose of study treatment, irrespective of whether some of these subjects may have discontinued treatment prior to the trial's end.

RP analysis set (**RPAS**)

The RPAS is defined as a subset of FAS, which includes all FAS subjects who actually received RP within 30 days by the end of NHT, regardless of prematurely discontinued treatment.

All RP related assessments will be conducted based on RPAS except for the primary analysis, where the denominator will be number of subjects in FAS.

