8.4 Outcome measures for analyses

8.4.1 Primary endpoint

Actual radical prostatectomy rate

Actual radical prostatectomy rate is defined as the rate of the subjects who perform radical prostatectomy within 30 days after end of NHT

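### The protocol's statistical section counts only prostatectomies within 30 days after end of NHT; the SAP sets no time limit for the primary endpoint or the RPAS, and the two need aligning before database lock

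*SAP*

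**What the plan says.** **With the limit.** Protocol 8.4.1 defines the primary endpoint as "the rate of the subjects who perform radical prostatectomy within 30 days after end of NHT". Protocol 8.3 defines the RPAS as "all FAS subjects who actually received RP within 30 days by the end of NHT, regardless of prematurely discontinued treatment".

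**Without the limit.** SAP 3.1 uses the "percentage of the subjects who actually received radical prostatectomy after receiving NHT, including those who early discontinued from treatment", with the FAS as denominator. SAP 2.1 describes the RPAS as a subset of the FAS "which included FAS subjects who actually received RP surgery". SAP 4.3.6, the primary analysis, refers only to surgery after NHT. Within the protocol, 5.1.1 has "the rate of the subjects who perform radical prostatectomy after NHT", and 8.5.1 also gives no window.

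**Follow-up of unoperated subjects.** Protocol 3.7.4 reads: "If the subjects who actually can not receive radical prostatectomy within 30 days after 24 weeks neoadjuvant therapy, it will be considered as completion". Footnote e of the protocol schedule (4.1) ends visits for these subjects once the reason for no surgery has been collected. Protocol 4.4 adds a safety visit 12 weeks after the last Zoladex dose. SAP 4.1 makes their end-of-study visit the same as the end-of-treatment visit.

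**Dates and declared changes.** The SAP is dated 13-01-2021 and protocol version 5.0 is dated 21 April 2021. The SAP's amendment history and its section 6 (changes from protocol) both read NA.

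**The concern.** This is the trial's only primary endpoint, and two programmers working from the two documents could report different values for it. A man operated on 40 days after end of NHT is a failure under protocol 8.4.1 and a success under SAP 3.1.

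The same man is outside the protocol's RPAS and inside the SAP's. That changes the denominator for surgical margins, seminal vesicle invasion, nodal involvement, downstaging, PSA below 0.1 ng/mL, continence and potency. Because the protocol has already closed his follow-up, he may enter those denominators without data. Under SAP 3.2 a subject with no post-surgery record is censored at day 1 for time to continence. His recorded reason for not being operated on also drops out of the reasons table, which covers only FAS subjects outside the RPAS.

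The two rules also differ in ascertainment. The 30-day rule matches the period over which every subject is followed. The open-ended rule has no common time at which surgical status is established.

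**Working it through.** **1. The plan's own precision figure.** Inputs from protocol 8.2 and SAP 1.3: N = 104, expected rate 90%, dropout 10%, two-sided 95% CI, half-width 6.1%.

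- Evaluable n = 104 × 0.9 = 93.6.
- Wald half-width = 1.96 × √(0.9 × 0.1 / 93.6) = 0.0608, or 6.1%. The figure is reproduced.
- In reverse, 1.96² × 0.09 / 0.061² = 92.9, so n = 93, and 93 / 0.9 = 103.3, so 104.

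The sample-size statement does not depend on which definition is used.

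**2. Direction.** Every operation inside the 30-day window also counts under the SAP. With the FAS as denominator in both documents, SAP rate ≥ protocol rate. They are equal only if no operation after day 30 is recorded.

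**3. Size.** Let k be the number of recorded operations after day 30. The documents do not give k, so it is an assumption. The difference is k/104. For illustration, take FAS = 104 and 94 operations in all, with Clopper-Pearson intervals (the method in protocol 8.5.1):

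| k (assumed) | Rate under the 30-day limit | 95% CI (%) | Difference from SAP rate (points) |
|---|---|---|---|
| 0 | 94/104 = 90.4% | 83.0 to 95.3 | 0 |
| 1 | 93/104 = 89.4% | 81.9 to 94.6 | 1.0 |
| 3 | 91/104 = 87.5% | 79.6 to 93.2 | 2.9 |
| 6 | 88/104 = 84.6% | 76.2 to 90.9 | 5.8 |

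The SAP rate is 90.4% in every row. Six late operations come close to the planned half-width of 6.1 points; seven (7/104 = 6.7 points) would exceed it. The RPAS shrinks from 94 to 94 − k.

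**4. Would a late operation be seen?** With implants on Day 1 and Day 85, the safety visit in protocol 4.4 falls on Day 85 + 84 = Day 169. That is the end-of-treatment visit itself, so it adds no contact after the window. For an early discontinuer it can fall later. For example (assumed), with one implant on Day 1 and end of treatment on Day 40, the safety visit is on Day 1 + 84 = Day 85, which is 45 days after end of treatment. Ascertainment after day 30 is therefore absent for most subjects and uneven for the rest.

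**5. When the 30 days start.** The protocol schedule puts end of treatment at Day 169 ± 5. SAP 4.1 puts it 12 weeks after the last injection, which it equates with V4 at 180 ± 10 (Day 170 to 190). With on-schedule dosing, 12 weeks after the last injection is Day 169, just outside that range. Counted from the nominal days, the window closes on Day 199 (169 + 30) or Day 210 (180 + 30). Adding the limit to SAP 3.1 alone would leave this 11-day gap.

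**The case against.** **The SAP may not have removed anything.** A reader might infer that the SAP loosened the endpoint. The documents do not support that. The SAP predates protocol version 5.0 by about three months, and the version it was written against is not available. The limit may have entered with version 5.0, in which case NA in SAP 6 was correct when written. Protocol 5.1.1 has no limit either. This objection stands: what is shown is a lack of alignment, not which text changed.

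**The rates may never differ.** The protocol asks for surgery within 30 days and then closes the study for unoperated subjects, so k may be 0. This also stands. The two harms are alternatives for any one late operation: if it is recorded, the two rates differ; if it is not, they agree, but the SAP numerator then misses an operation that its own definition counts.

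**The SAP has some safeguards.** SAP 4.1.1 places a visit at 180 ± 10 at which the reason for no surgery is recorded. SAP 2.2 lists separately the major deviations that could affect interpretation of the primary endpoint. Both make a late operation more visible, but neither says whether it counts in the numerator.

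**Nothing is tested.** The study is single-arm and descriptive, with no success threshold, so no pass/fail decision turns on the choice. That limits the consequence. It does not remove the need for one definition of the primary rate.

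**Conclusion.** The mismatch is on the face of the documents and should be resolved before database lock. Protocol 8.4.1 and 8.3 limit the primary numerator and the RPAS to 30 days after end of NHT. SAP 3.1, 2.1 and 4.3.6 do not, and neither do protocol 5.1.1 and 8.5.1.

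The effect is conditional: 0.96 points per recorded late operation if the FAS is 104, and nothing if there are none. The range of 1.0 to 5.8 points rests on an assumed 1 to 6 late operations and is not a forecast. The direction is certain: the open-ended rule can only equal or exceed the 30-day rule.

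A reader might also infer that no visit could ever detect a late operation. That is too strong, because the safety visit can fall after the window for early discontinuers. The supportable statement is that surgical status after day 30 is not systematically ascertained.

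**What to change.** - **SAP 3.1 and 4.3.6:** define the numerator as radical prostatectomy within 30 days after end of NHT, with all FAS subjects as denominator.
- **SAP 2.1:** adopt the RPAS of protocol 8.3.
- **Start of the 30 days:** give end of NHT one definition in both documents, including for early discontinuers, and reconcile SAP 4.1 and 4.1.1 (180 ± 10) with the protocol schedule (Day 169 ± 5).
- **Protocol 5.1.1 and 8.5.1:** add the limit so that the protocol agrees with itself.
- **SAP 6 and amendment history:** record the alignment with protocol version 5.0.
- **Sensitivity analysis:** report surgery at any recorded time, labelled as such, with a note that ascertainment after day 30 is incomplete.

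The cost is wording in both documents. It needs no new data and leaves the sample size unchanged; protocol 8.1 allows SAP amendments up to data lock. The downside is that the reported rate may be lower if late operations occur.

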3.2 SECONDARY ENDPOINT

• The mean PSA by the end of NHT and PSA change from baseline

The mean PSA by the end of NHT is defined as the average PSA level by the end of NHT where all non-missing PSA level records at each visit (up to end of treatment visit) will be summarized. PSA change from baseline is defined as the change of PSA level at each visit from baseline (at enrollment) value, and this value will only be derived if both baseline and post-baseline records are non-missing values. Post-surgical visits will only be summarized for RP analysis set.

• Percentage of positive surgical margins for primary tumor

Percentage of positive surgical margin of primary tumor is defined as the percentage of subjects with tumor at the margin positively resected in the postoperative pathological RP specimen. The denominator will be based on the RP analysis set.

• Incidence rate of seminal vesicle invasion and involvement rate of bilateral pelvic lymph nodes

Incidence of seminal vesicle invasion and involvement of pelvic lymph node is defined as the percentage of subjects with seminal vesicle invasion and those with unilateral or bilateral pelvic lymph node metastasis in the postoperative pathology of RP specimen. Denominator will be based on RP analysis set.

• Pathological downstaging rate

Pathological downstaging is defined as the tumor stage assessment has decreased from baseline pathology diagnosis records to post RP surgery assessment. Pathological downstaging rate will be derived as the percentage of pathological downstaging subjects out of all RP analysis set subjects.

• Rate of Post-surgical PSA decreased to the less than 0.1ng/ml

Rate of post-surgical PSA decreased to less than 0.1ng/ml referred to the percentage of subjects with any post-surgical follow-up records of serum PSA level < 0.1 ng/mL, including the termination visit, out of all RP analysis set subjects.

Surgical-related variables and complications

- Reason for not conducting the RP surgery will be summarized for those in FAS but not in RPAS, where percentage for each category of reasons will be derived with number of subjects in FAS as denominator. Missingness will be summarized as a separate category if applicable.
- Operative Duration is defined as the time (mins) from incision to finishing suturing, and will be derived based on the time difference from stop date/time to start date/time as recorded for the RP surgery.
- o Intraoperative Estimated Blood Loss will be estimated using haematocrit parameters collected during the RP surgery where results will be recorded in mL.
- o Duration of Indwelling Catheterization (Days) is defined as days from the start of surgery to removal of catheter

- Complications will be coded using Medical Dictionary for Regulatory Activities (MedDRA Version 23.0 or later). Where results will be summarized as the percentage of subjects who experience complications and percentage of subjects with complications needing intervention, based on RP analysis set.
- Our Urine function will be measured by dichotomous outcomes (continence or incontinence), which incontinence is primarily defined as the use of pads or absence of leakage. Time to Continence (Days) and urinary continence rate at 12 weeks after surgery will be reported. Time to Continence (Days) is defined as days from surgery to the earliest recorded date of continence during post-surgical follow-up period. Subjects who remained incontinence or with missing urine function records at the time of analysis will be censored at his latest visit day with non-missing urine function record. Subjects with no post-surgery records will be censored at day 1. While for continence rate at 12 weeks, missingness will summarized as a separate category.
- Erectile function will be measured by dichotomous outcomes (potent or impotent). Potent or not will be primarily determined by a single question raised by investigator at week 12 visit after RP surgery on whether the patient has experienced erections sufficiently firm for sexual intercourse. Potent rate is defined as the proportion of the subjects who are assessed as potent out of all RP analysis set subjects.
- AEs will be coded using Medical Dictionary for Regulatory Activities (MedDRA V23.0 or above). Summary for AEs will be presented by System Organ Class (SOC) and Preferred Term (PT), where details of analysis will be described in next section.

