4 STUDY PLAN AND TIMING OF PROCEDURES

4.1 Study schedule

Visit	1	2	3	4	5 ^e	6	7	8 ^g	For
Day	-28 to -1	1	85	169/E nd of treatm ent	EOT+30	RP+30	RP+90	Study completio n/disconti nuation	details see Protocol Section
Visit window	_	±5d	±5d	±5d		±5d	±5d	±5d	
Written informed consent	X								4.2
Demographics	X								4.2
Physical examination	X	Xa							4.2
Medical/surgical history	X								4.2
Inclusion/exclusion criteria	X								4.2
ECOG performance status	X	Xa	X	X	Xª		X	X	4.2, 4.3 & 4.4
Vital signs, body weight	X	Xa	X	X	Xª		X	X	4.2
ECG	X	Xa			Xa				4.2
Imaging (CT or MRI)	x					X (clinical ly indicated)	X (clinical ly indicated)	X (clinical ly indicated)	4.2, 4.3 & 4.4
Bone scan	X								4.2, 4.3 & 4.4
Gleason score	X				X				4.2 & 4.4
Zoladex and Casodex treatment		Xc	Xc						4.3
RP evaluation				X					4.3
RP					X				4.4
Assessment after radical prostatectomy plus ePLND					X				4.4
ADT after RP						X ^b	Xb	X ^b	4.4

Visit	1	2	3	4	5°	6	7	8 ^g	For
Day	-28 to -1	1	85	169/E nd of treatm ent	EOT+30	RP+30	RP+90	Study completio n/disconti nuation	details see Protocol Section
Visit window	-	±5d	±5d	±5d		±5d	±5d	±5d	
Concomitant medication	X	X	X	X	X	X	X	X	4.2, 4.3 & 4.4
Adverse event	X	X	X	X	X ^d	X ^d	X ^d	X ^d	4.3 & 4.4
Haematology and clinical chemistry	X	Xa	X	X		X	X	X	4.2, 4.3 & 4.4
Blood germline forHRRm collected				X(all patien ts)					4.3
Tumor tissue for HRRm collected					X ^h				4.4
Urinalysis	X	Xa							4.2
Serum testosterone level	X	Xa	X	X		X	X	X	4.2, 4.3 & 4.4
Serum PSA level	X	Xa	X	X		X	X	X	4.2, 4.3 & 4.4

a. If assessed within 7 days before enrolment and meets the stated eligibility criteria (if applicable), it does not need to be repeated on Day 1 of study treatment unless investigator believes that it is likely to have changed significantly.

b. The treatment will be based on investigator's discretion

c. Casodex will be administrated till Week 24

d. AEs will be actively collected from ICF to 12 weeks after last dose of Zoladex

e. Radical prostatectomy should be performed within 30 days after end of NHT. The visit will be ended for the patients without radical operation following NHT after collection of the reason for failure to receive an operation.

f. The visit will be completed after follow-up for three months following radical operation

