4.2 Enrolment/screening period

Procedures will be performed according to the Study Plan. Written informed consent for participation in the study must be obtained before performing any study-specific screening tests or procedures.

At screening, consenting subjects are assessed to ensure that they meet eligibility criteria. Subjects who do not meet these criteria must not be enrolled in the study. Screening and pretreatment tests will be performed within 28 days preceding Day 1 (defined as the day of first dose of study drug). Results of standard of care tests performed prior to obtaining informed consent and within 28 days prior to study entry may be used; such tests do not need to be repeated for screening.

The study procedures carried out during this period include: demographics, physical examination, medical/surgical history, ECOG performance status, vital signs, body weight, ECG, Imaging (CT or MRI), bone scan, Gleason score, concomitant medication, haematology and clinical chemistry, urinalysis, serum testosterone level and PSA level. Results must be judged and confirmed by the investigator prior to study drug administration on Day 1.

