4.3 Treatment period

Descriptions of the procedures for this period are included in the Study Plan with exceptions of the following specific requirements for the treatment period:

All visits must occur within \pm 5 days starting at visit 2 from the scheduled date. All assessments will be performed on the day of the specified visit unless a time window is specified.

ECOG performance status and weight will be performed at Day 1, Day 85, or Day 169/at end of treatment visit.

Haematology and Serum chemistry will be tested at Day 1, Day 85, or Day 169/at end of treatment visit. Additional monitoring for haematology and serum chemistry will be provided as clinically indicated.

Serum PSA level and testosterone level will be collected at Day 1, Day 85 or Day 169/at end of treatment visit.

Assessment of subject's eligibility for radical prostatectomy will be performed in all enrolled subjects by investigators at Day 169/at end of treatment visit as well as blood sample for germline HRR mutation testing of all enrolled subjects will be collected. If scheduled study assessments cannot be obtained because of a holiday, these assessments should be obtained at the soonest following date, unless the soonest following date is not more than 2 days away from the evaluation time of other planned studies.

If the information as the ECOG performance status, haematology, serum chemistry, serum PSA, testosterone, concomitant medications has been collected within one week prior to the end of treatment visit, it will no more be collected, unless it is considered by the investigator that relevant information will be significantly changed in a short period.

Investigators can suggest patients to take regular serum transaminase test in the outpatient department of hospital for the first four months of treatment with Casodex and then periodically, followed clinical practice or as clinical indicated. Management of abnormal results of serum transaminase that causally related to Casodex please follow the guidance in Section 6.10.

If the dose of Zoladex (Goserellin acetate implant) is delayed by more than 7 days during ontreatment period, early termination of study treatment will be considered. If Zoladex is permanently discontinued, Casodex should be permanently discontinued.

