8.4.2 Secondary endpoints

• The mean PSA at the end of NHT and PSA change from baseline

- Percentage of positive surgical margins for primary tumour
- Incidence rate of seminal vesicle invasion and involvement rate of pelvic lymph nodes
- Pathological downstaging rate
- Rate of post-surgical PSA decreased to less than 0.1ng/ml

Surgical-related variables and complications Operative Duration is defined as the time (mins) from incision to finishing suturing.

Intraoperative Estimated Blood Loss will be calculate using haematocrit parameters collected during the operation and measured as a continuous variable.

Duration of Indwelling Catheterization (Days) is defined as days from the start of surgery to removal of catheter.

Complications will be presented as the percentage of subjects who receive RP and experience complications and percentage of subjects for complication needing intervention will be calculated.

Urine function will be measured by dichotomous outcomes (continence or incontinence), which outcomes are defined as primarily the use of pads or absence of leakage. Time to Continence (Days) and urinary continence rate at 12 weeks after surgery will be reported.

Erectile function will be measured by dichotomous outcomes (potent or impotent). Outcome results will be primarily determined by a single question will ask patients if they experience erections sufficiently firm for sexual intercourse. Potent rates in erectile function at 12 weeks after surgery will be calculated.

• AEs

Definition and reporting of AEs is referred to Section 6. AEs will be coded using Medical Dictionary for Regulatory Activities (MedDRA). Summary for AEs will be presented by System Organ Class (SOC) and Preferred Term (PT).

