8.5.2 Analysis of the secondary variable(s)

- PSA levelwill be summarised by the number of person (n), mean, median, SD, minimum, and maximum at each time points.
- The resection margin status (positive), seminal vesicle invasion, involvement of pelvic lymph nodes, pathological downstaging and rate of subjects with post-surgical PSA decreased to the less than 0.1ng/ml will be summarised by frequency counts and percentages.
- Surgical variables and complications will be summarized either by the number of observations (n), mean (or geometric mean if appropriate), SD, median, quartiles (Q1 and Q3), minimum, and maximum, or by frequency counts and percentages for each category.
- All AEs, serious AEs (SAEs), drug related AEs, and AEs leading to study drug discontinuation will be summarised by Medical Dictionary for Regulatory Activities (MedDRA) preferred terms and CTCAE grade.
- Treatment-emergent AEs, i.e., the AEs occurring on or after the first dosing of study drug and up to 4 weeks after discontinuation of study drug, will be included in the AE summaries.

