4.3.7 Analysis of the secondary variable(s)

4.3.7.1 PSA level, mean PSA level by the end of NHT, resection margin status, seminal vesicle invasion, involvement of bilateral pelvic lymph nodes ,pathological downstaging and rate of post-surgical PSA decreased to less than 0.1ng/ml

PSA level will be summarized by visit, and change from baseline value will be summarized for post-baseline visits. PSA level and average PSA level by the end of NHT will be analysed based on FAS. While other variables will be summarized using descriptive statics based on RP analysis set. Shift table for pathological stage between baseline and post-surgery assessment might be provided as applicable.

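### The SAP defines the protocol's mean PSA at the end of NHT as an average by the end of NHT, which can be read as mixing in earlier, even pre-treatment, PSA records

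*SAP*

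**What the plan says.** **Protocol.** The synopsis, section 2.2 and section 8.4.2 all put this first among the secondary endpoints: "The mean PSA at the end of NHT and PSA change from baseline". Section 8.5.2 summarises PSA by "mean, median, SD, minimum, and maximum at each time points". No average across visits appears in the protocol.

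**SAP.** Section 3.2 defines the endpoint as "the average PSA level by the end of NHT where all non-missing PSA level records at each visit (up to end of treatment visit"; the sentence closes by saying that these records will be summarised. It sets an upper limit on the records used but no lower one. It does not say whether a subject's records are combined into one value, or whether pre-treatment records count. Section 4.3.7.1 states "PSA level will be summarized by visit, and change from baseline value will be summarized for post-baseline visits", and then "PSA level and average PSA level by the end of NHT will be analysed based on FAS". The SAP uses 'by' for this endpoint three times in 3.2 and twice in 4.3.7.1, so it is not an isolated slip. Section 6, on changes from the protocol, lists none.

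**PSA schedule.** The screening tests in Protocol 4.2 include "urinalysis, serum testosterone level and PSA level". Protocol 4.3 adds: "Serum PSA level and testosterone level will be collected at Day 1, Day 85 or Day 169/at end of treatment visit". Footnote a to the schedule in Protocol 4.1 makes the Day 1 sample optional if PSA was assessed within 7 days before enrolment: "it does not need to be repeated on Day 1 of study treatment", unless the investigator expects a significant change.

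**The concern.** The protocol asks for PSA at one time point. The SAP attaches the endpoint's name to an average with no stated lower limit on the records, and lists it as an item beside by-visit PSA. If it were only the by-visit mean at the last treatment visit, the second item would be redundant.

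At stake is what gets reported under the endpoint's name. An average that includes records from before or midway through treatment does not describe the PSA reached after 24 weeks of NHT. It would also depend on how many pre-treatment samples a subject happened to have. Two programmers could follow the same text and produce quite different figures, and nothing in the SAP would settle which one is the endpoint.

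**Working it through.** **Plan's own figure.** The documents state no expected PSA and no precision for this endpoint. The only design figure (104 subjects, 6.1% half-width) concerns the primary endpoint. It reproduces: 1.96² × 0.9 × 0.1 / 0.061² = 92.9, rounded up to 93, and 93 / 0.9 = 103.3, rounded up to 104. It has no bearing here.

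**Inputs from the documents.** Up to the end-of-treatment visit a subject has one or two pre-treatment PSA records (screening, and Day 1 unless skipped), one at Day 85 and one at Day 169/end of treatment. That makes three or four records.

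**Formulas.** Set baseline PSA to 1, and take screening and Day 1 as equal when both exist. Let r1 be PSA at Day 85 and r2 PSA at end of treatment, both as fractions of baseline. The protocol endpoint is r2. The possible averages are:

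- four records: (2 + r1 + r2) / 4
- three records: (1 + r1 + r2) / 3
- post-baseline records only: (r1 + r2) / 2

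**Floor.** With r1 = r2 = 0, the four-record average is 2/4 = 50% of baseline and the three-record average is 1/3 = 33%. Neither can go lower, whatever happens on treatment.

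**Size under assumed falls.** The values of r1 and r2 below are assumptions chosen to span steep to shallow falls. Each entry is the average divided by r2.

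| r1, r2 (assumed) | Four records | Three records | Post-baseline only |
|---|---|---|---|
| 2%, 0.5% | 0.50625 / 0.005 = 101 | 0.3417 / 0.005 = 68 | 0.0125 / 0.005 = 2.5 |
| 5%, 1% | 0.515 / 0.01 = 51.5 | 0.3533 / 0.01 = 35.3 | 0.03 / 0.01 = 3.0 |
| 10%, 5% | 0.5375 / 0.05 = 10.75 | 0.3833 / 0.05 = 7.7 | 0.075 / 0.05 = 1.5 |
| 30%, 20% | 0.625 / 0.20 = 3.1 | 0.50 / 0.20 = 2.5 | 0.25 / 0.20 = 1.25 |
| 50%, 50% | 0.75 / 0.50 = 1.5 | 0.6667 / 0.50 = 1.3 | 0.50 / 0.50 = 1.0 |

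**Dependence on scheduling.** In the second row, two men with the same PSA course score 51.5% or 35.3% of baseline, depending only on whether Day 1 PSA was repeated. Pre-treatment records supply 2/2.06 = 97% or 1/1.06 = 94% of the sum.

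**Which record is the end of NHT.** Protocol 4.1 puts Visit 4 at Day 169 ± 5, that is Days 164 to 174. SAP 4.1 puts V4 at Day 180 ± 10, that is Days 170 to 190. The windows share only Days 170 to 174. SAP 4.1.1 also gives 180 ± 10 for the visit after the operation, so the day alone does not show whether a record is pre-operative.

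**The case against.** The strongest reply is that the SAP sentence need not mean a cross-visit average. It says that records at each visit will be summarised, which can describe an average across subjects, tabulated by visit. The only PSA method that 4.3.7.1 spells out is by visit. The sentence naming the average mainly assigns the analysis set, and no per-subject formula is given anywhere. This stands as a genuine ambiguity. It does not remove the defect, because the SAP still does not say which figure is the protocol's endpoint.

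A reader might infer that the SAP has replaced the endpoint and that earlier values swamp the end-of-NHT result by dozens of times. The documents do not support that. The by-visit table yields the end-of-treatment mean, and change from baseline at that visit, on either reading. The large multiples need pooling, inclusion of pre-treatment records and a steep assumed fall all together. Mid-treatment values alone inflate the figure by at most 3.0 times in the assumed cases.

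A reader might also infer that early drop-outs contribute only high early values. The schedule has PSA at the end-of-treatment visit and at the study discontinuation visit, so a man who stops early and attends has a later value. Only someone with no PSA after the start of treatment would contribute pre-treatment values alone.

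Finally, the SAP is dated 13 January 2021, before protocol version 5.0 of 21 April 2021, and the protocol wording then in force is not visible. The absence of a declared change therefore carries limited weight, but the two current documents still disagree.

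**Conclusion.** The point holds as a mismatch of definition. The protocol endpoint is PSA at the end of NHT, while the SAP gives the endpoint's name to a variable defined over all records up to that visit, without declaring a change. On the cross-visit reading this is a different quantity.

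The floor of 33% or 50% of baseline rests only on pre-treatment records being counted, all scheduled records being present, and screening and Day 1 values being equal where both exist. The multiples of about 1.3 to 101 (pre-treatment records included) and 1.0 to 3.0 (post-baseline only) rest on assumed PSA falls and illustrate the range; they do not predict this trial's result.

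This should be fixed before database lock. It is not critical: the endpoint is descriptive, nothing is tested on it, and the primary endpoint does not depend on it.

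**What to change.** 1. In SAP 3.2 and 4.3.7.1, define the endpoint as each subject's PSA value at the end-of-treatment visit (V4, before radical prostatectomy), summarised across FAS subjects, with change from baseline at that visit.
2. Delete the cross-visit average. If the sponsor wants to keep it, give it a separate name, state how records are combined and whether pre-treatment records count, and declare it in SAP section 6.
3. Reconcile the V4 timing in Protocol 4.1 with SAP 4.1 and 4.1.1, so that one rule identifies the end-of-NHT record.

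No extra summary statistics are needed: SAP 4.1 already provides the median and allows a geometric mean where appropriate. The cost is SAP wording and one derivation, plus whatever wording change the timing reconciliation needs. No new data are required.
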